Endpoints for Evaluation:

Primary: To compare the relationship of once daily tacrolimus extended release (Envarsus) versus twice daily tacrolimus immediate release (Prograf) doses to achieve target trough concentrations (C) relative to the total daily dose (D) given

and the effect of C/D ratio on renal function at day 7 and months 1, 3, 6, and 12 months after transplantation utilizing concentration to dose ratio (C/D ratio).

Secondary: Comparison between treatment cohorts regarding incidence will rely upon assessments for each of the following results:

- Compare incidence of rejection between the groups at 90 and 365 days post-transplant (Banff grade I-III and antibody mediated rejection [AMR])
- Compare graft loss and death within 1 year post-transplant
- Compare and summarize serious adverse events (AEs) between study groups
- Death within 1 year post-transplant

Statistical Analysis:

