Sample Size: The sample size for this pilot study is not sufficiently powered to document that the C/D ratio in each patient group will correlate directly with eGFR. We expect to see a trend suggestive that the Envarsus group by virtue of more stable Tacrolimus level and greater compliance over time will be less likely to develop calcineurin-induced nephrotoxicity and therefore result in a better e-GFR. This is not likely to be statistically significant in this inadequately powered study since the variability in donor organs themselves, as well as many other variables, will not permit a precise analysis in this small study sample. However, stratification for living donors and deceased donors may provide important trends in this pilot project which may then guide us to expand the study in more restricted categories of renal allograft recipients. The statistical summary and analysis of safety data, will consist of all subjects who enrolled into the study and took at least one dose of study medication. Demographics and other baseline characteristics will be summarized by treatment group. Descriptive statistics (e.g., n, mean, standard deviation, minimum, median, maximum) and interquartile range, coefficient of variation, and geometric mean will be provided for tacrolimus dose and whole blood concentrations of tacrolimus for both study cohorts. Tacrolimus concentrations will be summarized with descriptive statistics. The analysis of efficacy regarding C/D effectiveness in relation to number of rejection episodes and outcomes at various stated time points will be conducted using Student T test. The association between whole blood concentrations and the following endpoints will be assessed: rejection episode and eGFR, histopathology (Banff classification) and conventional measures of transplant outcomes.

H0: The probability of incidence for the primary endpoint is the same between patients receiving Envarsus and patients receiving immediate-release tacrolimus.

Safety: All adverse events (AE) will be listed. The number and percentage of AEs, significant AEs, AEs leading to discontinuation, and AEs related to study drug will be summarized by treatment group. The number and percentage of AEs by severity will also be summarized.

Randomization will be performed in excel prior to initiation: Allocation will consist of a 1:1 ratio for twice daily, immediate-release tacrolimus or Envarsus.

Institutional Review Board (IRB)

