Medical History: Etiology of renal failure, viral serology (HBV, HCV, CMV, EBV), and diabetes history (as applicable). *Transplant Information*: Day 0 visit: type of transplant (living related, living non-related, DD, and whether organ was obtained in the setting of DCD or CDC), number of prior transplants and reason for prior graft loss (if applicable), total cold and warm ischemia time in hours and minutes, KDPI, ABO blood typing, HLA typing of donor and recipient, degree of HLA mismatch between donor and recipient, and most recent panel reactive antibody testing. Donor viral serology information (HBV, HCV, CMV, EBV), if available, will be collected and recorded. Additional donor information includes age, sex, height, weight, donor cause of death, ethnicity, ABO typing, and results of any pre-implantation biopsies. *Height and Body Weight*: Height and dry weight will be recorded at screening and pre-operatively on study day 0.

Efficacy Assessment

Estimated Glomerular Filtration Rate: Estimated glomerular filtration rate (eGFR) will be calculated at day 7 and months 1, 3, 6, and 12 using the Modification of Diet in Renal Disease (4 variable – MDRD) criteria.

Calculation of C/D Ratio: Calculation of the daily trough level over the average daily total tacrolimus dose delivered either by ENVARSUS or by SOC twice a day Tacrolimus will be performed monthly throughout the study.

Patient Survival: Patient survival is any subject that is known to be alive at the study conclusion.

Graft Survival: Graft survival is defined as any subject that does not fit the following definition of graft loss: subject death, re-transplantation, transplant nephrectomy, or return to dialysis for a period of ≥6 weeks by study end. *Acute Rejection*: For study purposes, diagnoses of rejection require biopsy confirmation. Both acute cellular and antibody mediated rejection will be assessed and graded according to published criteria [Solez et al, 2008] by the NYPH

Renal Pathology Division pathologist.

Adverse Events

Adverse event collection will begin once informed consent has been signed and continue throughout the subject's participation in the study. A subset of the routine laboratory assessments obtained per SOC, including creatinine, hemoglobin, hematocrit; platelet count; white blood cell count; serum sodium, potassium, blood urea nitrogen, glucose, urinalysis (including urinary protein), tacrolimus trough concentrations.

Physical Examination

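### The effect of C/D on eGFR is part of the primary endpoint, but the only test named for C/D is an ungrouped t test, and no C/D is assigned to the day-7 eGFR

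*Combined protocol and SAP*

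**What the plan says.** The Primary Objective and the Endpoints for Evaluation section give the primary endpoint two parts: an arm comparison of trough relative to total daily dose, and "the effect of C/D ratio on renal function at day 7 and months 1, 3, 6, and 12 months after transplantation". The Study Design section repeats both.

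The Statistical Analysis section contains these statements that bear on the second part:

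- The efficacy analysis of "C/D effectiveness in relation to number of rejection episodes and outcomes at various stated time points will be conducted using Student T test". The groups to be compared are not stated.
- "The association between whole blood concentrations and the following endpoints will be assessed: rejection episode and eGFR", among other endpoints. The predictor is concentration, and no method is named.
- The sample is "not sufficiently powered to document that the C/D ratio in each patient group will correlate directly with eGFR". This is a remark on power, with no analysis attached.
- Descriptive statistics "will be provided for tacrolimus dose and whole blood concentrations of tacrolimus for both study cohorts". The ratio itself and eGFR are not listed.
- "stratification for living donors and deceased donors may provide important trends in this pilot project".

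The Efficacy Assessment section sets eGFR (4-variable MDRD) at day 7 and months 1, 3, 6 and 12. It defines C/D as "Calculation of the daily trough level over the average daily total tacrolimus dose delivered", calculated monthly, and gives no averaging window for the dose. Follow-up visits are monthly, and the Schedule of Events goes from Day 0 to Month 1.

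**The concern.** The endpoint asks how one continuous measure, C/D, relates to another, eGFR, at five times. A Student t test compares two group means, so it answers that question only once C/D has been cut into two groups, and the plan gives no cut. The analyst is left to choose between an arm contrast, a split of C/D and a concentration association. These estimate different things, and none is an efficient estimate of the relation in the endpoint.

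Concentration is a poor stand-in for the ratio. The dosing sections have both arms titrated to the same minimum trough, so differences between patients in the dose needed to reach it show up in D and therefore in C/D, not in C alone.

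The timing is a smaller, separate gap. For one of the five eGFR times, nothing says which trough and which days of dosing make up the C/D value. That matters because dose is adjusted after the initial weight-based dose, so the ratio may depend on the window chosen.

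At stake is whether the pilot reports a defined estimate, with its uncertainty, for this part of its primary endpoint.

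**Working it through.** **Does each planned analysis reach the endpoint?**

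| Planned item | Estimates the C/D–eGFR relation? |
|---|---|
| t test, grouped by arm | No: gives the arm difference |
| t test, grouped by a C/D cut | Yes, as a two-group contrast, but no cut is stated |
| Association of concentration with eGFR | No: C without D |
| Remark on power for a C/D–eGFR correlation | No method given |

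**Arm t test.** Simulation: 5,000 trials, 25 per arm, standard normal C/D and eGFR, no arm difference in either, two-sided 5% level (assumed).

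| True C/D–eGFR correlation | Arm t test on eGFR rejects | Correlation test rejects |
|---|---|---|
| 0 | 5.4% | 5.8% |
| 0.3 | 5.2% | 57.0% |
| 0.6 | 5.7% | 99.8% |

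The arm test does not respond to the relation. This depends on C/D not differing by arm. If it does differ, the arm contrast in eGFR mixes any C/D effect with every other effect of formulation and still does not isolate the relation.

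**Median split.** For a normal variable, the information kept is 2/π = 0.637. With 50 patients, 50 × 0.637 = 31.8, as if about 32 patients had been studied with C/D left continuous.

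**Precision of a regression slope at one time.** From the document: n = 50, 25 per arm. Assumed, because the documents give no SDs: SD of log C/D 0.5 (range 0.4–0.6) and residual eGFR SD 17 (range 15–20) mL/min/1.73 m².

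Half-width of the 95% CI = t(0.975, df) × residual SD / (SD of log C/D × √(n − 1)).

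- n = 50, df 48: 2.011 × 17 / (0.5 × 7) = 9.77 per log unit.
- Range: 2.011 × 15 / (0.6 × 7) = 7.18 to 2.011 × 20 / (0.4 × 7) = 14.36.
- Data on 45 patients: 10.34. Data on 40: 11.02.
- Median split on the same scale: 9.77 / √0.637 = 12.24.
- One arm of 25, df 23: 2.069 × 17 / (0.5 × 4.899) = 14.36 (range 10.56–21.11).

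**Adjusting for arm and donor type.** Changing only the degrees of freedom (df 46) gives 2.0129 × 17 / 3.5 = 9.777. That assumes C/D is unrelated to arm and donor type, yet the Background section hypothesises that Envarsus raises C/D. With total SD held at 0.5 and an arm difference d in log C/D under 1:1 allocation, the share of variance left within arms is 1 − (d/2)²/0.25.

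- d = 0.3: 1 − 0.0225/0.25 = 0.91, and 9.777 / √0.91 = 10.25, or about 10.2.
- d = 0.5: 1 − 0.0625/0.25 = 0.75, and 9.777 / √0.75 = 11.29.

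**Timing.** eGFR falls at day 7 and months 1, 3, 6 and 12. Monthly C/D covers the last four, so 4 of 5 times have a scheduled value.

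**The case against.** A reader might infer that the plan contains no analysis at all of C/D against eGFR. The text does not support that. The t test is assigned to outcomes at stated times, eGFR is listed first under Efficacy Assessment, and the times stated for renal function are these five. On a natural reading eGFR is among the outcomes, and a split by C/D would estimate the relation crudely. What stands is narrower: the grouping is unstated, and a t test suits a continuous C/D poorly.

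A reader might also infer that a day-7 C/D cannot be obtained, or that dose is not recorded. Neither follows. The Adverse Events section lists routine creatinine and tacrolimus troughs, the C/D definition needs the delivered dose, dose summaries are planned, and medications are reviewed. The day-7 ratio is probably computable. What is missing is a rule for which trough and which dose window.

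The protocol is a declared pilot, admits low power and looks only for trends. That excuses a wide interval, but it does not say how the trend in a primary-endpoint component is to be estimated.

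Finally, a repeated-measures model with slopes at every time, overall and within each arm, would be more than this gap requires in 50 patients. That objection is accepted, and a regression at each time is enough.

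**Conclusion.** The concern holds in this limited form. For the C/D–eGFR part of the primary endpoint, the plan names a test without its grouping. By arm, that test misses the relation; after a median split, it keeps about 64% of the information if C/D is normally distributed. The only association naming eGFR uses the wrong exposure. The day-7 eGFR has no assigned C/D.

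The gap is visible in the text and does not depend on the assumed SDs; only the precision figures do. On those assumptions a single-time slope has a half-width of about 9.8 per log unit without an arm difference in C/D, and about 10.2 to 11.3 with one of 0.3 to 0.5. The slopes will be imprecise, which fits a pilot.

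The stated H0 ("The probability of incidence for the primary endpoint is the same between patients receiving Envarsus and patients receiving immediate-release tacrolimus") concerns an incidence compared between arms. Its wording is a separate issue and adds no weight here. The change should be made; it is cheap and does not bear on the sample size.

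**What to change.** 1. Keep the t test and say that it is for the arm contrasts in C/D and in eGFR. The planned concentration associations can stay.
2. Add, as exploratory estimates, a linear regression of eGFR on C/D as a continuous variable (for example log C/D) at day 7 and months 1, 3, 6 and 12, adjusted for arm and donor type (living or deceased). Report each slope with its 95% CI and make no significance claim. Within-arm slopes and a repeated-measures version are optional.
3. State that the arm-adjusted slope is an association, not the effect of formulation, which comes from the arm contrasts.
4. State which trough and which dose window define C/D at each eGFR time, including day 7, and list these items for abstraction from the standard-of-care record.

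The cost is some analysis wording, a simple model at each time, and the abstraction of trough and dose at five times. No patients or visits are added. The downside is that the slopes are imprecise and five times invite chance findings, so the results should be presented as estimates only.

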Official Title: To Understand the Impact of Immunosuppression Using Once-perday Envarsus XR on the Effect of Total Tacrolimus Dose/Trough Level Ratio on Renal Function (eGFR) in Kidney Transplantation

Unique Protocol ID: AAAR6805

Registration Identifier: NCT03511560

Document Date: June 11, 2019

Primary Objective: To compare the relationship of once daily tacrolimus extended release (Envarsus) versus twice daily tacrolimus immediate release (Prograf) doses to achieve target trough concentrations (C) relative to the total daily dose (D) given and the effect of C/D ratio on renal function at day 7 and months 1, 3, 6, and 12 months after transplantation utilizing concentration to dose ratio (C/D ratio).

Secondary Objective:

- Compare incidence of rejection between the groups at 90 and 365 days post-transplant (Banff grade I-III and antibody mediated rejection [AMR])
- Compare graft loss and death within 1 year post-transplant
- Death within 1 year post-transplant
- Compare and summarize serious adverse events (AEs) between study groups

Study Population: Living or deceased donor kidney transplant recipients 18 to 80 years of age.

Number of Subjects to be Enrolled / Randomized: 50 patients [25 patients in each arm]

Study Design Overview:

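### No method is given for the between-arm comparisons of rejection, graft loss and death, and the only test named, a Student t test, handles sparse yes/no data at 25 per arm poorly

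*Combined protocol and SAP*

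**What the plan says.** The opening summary sets the size at "50 patients [25 patients in each arm".

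Under Endpoints for Evaluation, the secondary list opens with "Comparison between treatment cohorts regarding incidence will rely upon assessments for each of the following results". The items include "Compare incidence of rejection between the groups at 90 and 365 days post-transplant" and "Compare graft loss and death within 1 year post-transplant". No test or interval is attached to any of them. The Efficacy Assessment section defines graft loss as "subject death, re-transplantation, transplant nephrectomy, or return to dialysis for a period of ≥6 weeks by study end", so the risk of graft loss is at least the risk of death.

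The Statistical Analysis section has one sentence on testing. Its subject is "The analysis of efficacy regarding C/D effectiveness in relation to number of rejection episodes and outcomes", and it ends by assigning the test: "outcomes at various stated time points will be conducted using Student T test". The same section plans an association analysis with no named method, and summarises adverse events by number and percentage. It states H0 as "The probability of incidence for the primary endpoint is the same between patients receiving Envarsus" and patients on the comparator. No alpha, confidence level, confidence interval or expected event rate appears anywhere.

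**The concern.** Rejection by day 90 and day 365, graft loss and death are each a yes or a no for each patient. A test of means on 0/1 data works tolerably when events are common, but these endpoints may be rare and each arm has 25 patients. A reader looking for the planned method finds only the t test. If it is used, a result of no events in either arm gives no statistic and an interval of zero width. That could be reported as no difference with no uncertainty attached. With a handful of events the interval looks more precise than the data allow.

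The trial calls itself a pilot meant to guide a larger study, so its useful output is estimates with honest uncertainty.

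The wording of H0 adds a second, separate difficulty. It concerns a probability of incidence for the primary endpoint, yet the primary endpoint concerns the C/D ratio and renal function, which are continuous.

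**Working it through.** The plan states no power or precision figure, so there is none to reproduce.

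**Inputs.** From the documents: n = 25 per arm and the Student t test. Assumed: a two-sided 5% level and event risks from 1% to 20% per arm.

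**1. Chance that the t test cannot be computed.** With no event in either arm both variances are zero and the statistic is 0/0. At equal risk p the probability is (1 - p)^50.

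| Assumed risk per arm | Probability of 0 v 0 |
|---|---|
| 1% | 0.99^50 = 60.5% |
| 2% | 0.98^50 = 36.4% |
| 4% | 0.96^50 = 13.0% |
| 5% | 0.95^50 = 7.7% |
| 10% | 0.90^50 = 0.5% |

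For 0/25 the Wilson upper limit is 3.8416/(25 + 3.8416) = 13.3%, so the Newcombe interval for 0 v 0 is -13.3 to +13.3 points.

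**2. Intervals with few events.** The pooled variance is [25a(1 - a) + 25b(1 - b)]/48, where a and b are the observed risks. The SE is the square root of (variance × 2/25), and the critical value on 48 df is 2.011.

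- 1 v 0: variance = 25 × 0.04 × 0.96/48 = 0.020; SE = 0.040; interval 4.0 ± 8.0, or -4.0 to +12.0 points. The Wilson limits are 0.7% to 19.5% for 1/25 and 0% to 13.3% for 0/25. Newcombe lower limit: 4.0 - √[(4.0 - 0.7)² + 13.3²] = -9.7. Upper limit: 4.0 + (19.5 - 4.0) = +19.5.
- 4 v 0: variance = 25 × 0.16 × 0.84/48 = 0.070; SE = 0.0748; t = 0.16/0.0748 = 2.14, p = 0.038; interval +1.0 to +31.0 points. Fisher's exact test gives p = 0.110. With Wilson limits of 6.4% to 34.7% for 4/25, Newcombe gives 16.0 - √[(16.0 - 6.4)² + 13.3²] = -0.4 up to +34.7, which includes zero.

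The 4 v 0 case is borderline, and score methods differ on it. The Miettinen-Nurminen statistic at zero difference uses a pooled risk of 4/50 = 0.08 and variance 0.08 × 0.92 × (2/25) × (50/49) = 0.00601. Then z = 0.16/0.0775 = 2.06, above 1.96, so that interval excludes zero.

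**3. Type I error of the t test at equal risks**, by enumeration of all 26 × 26 outcomes: 0.02% at 1%, 0.2% at 2%, 2.0% at 5%, 4.9% at 10%, 5.5% at 20%.

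**4. Coverage of a nominal 95% t interval at unequal risks**, by the same enumeration:

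| True risks | Coverage, zero-width counted as a miss | Probability of 0 v 0 | Coverage given at least one event |
|---|---|---|---|
| 1% v 4% | 71.7% | 28.0% | 99.6% |
| 1% v 5% | 77.6% | 21.6% | 99.0% |
| 2% v 6% | 85.1% | 12.8% | 97.6% |
| 2% v 8% | 86.8% | 7.5% | 93.8% |
| 5% v 10% | 91.6% | 2.0% | 93.5% |

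Newcombe coverage is at least 99.5% in the first four rows and 97.9% in the last. At equal risks the t interval covers 99.8% (2%), 98.0% (5%) and 95.1% (10%), if a zero-width interval at zero counts as covering.

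**The case against.** The plan does not clearly apply the t test to these endpoints. The subject of the sentence is C/D effectiveness. One natural reading is that C/D, a continuous measure, will be compared between patients with and without an outcome, and a t test is not wrong in kind for that. Graft loss and death are not named there. This stands, and it rules out saying that the plan uses a wrong test for them. On that reading, however, the incidence comparisons have no method at all, so the section needs the same addition.

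A reader might infer that the t interval covers far below 95% for rare events, or that the t test inflates false positives. The documents promise no interval. At equal rare risks the interval over-covers and the test is conservative. At the rarest unequal risks the shortfall is almost entirely the 0 v 0 case: at 1% v 4%, 28.0 of the 28.3 points missed. Once any event occurs, coverage in the pairs shown is 93.5% or better. Low coverage is therefore mostly the non-computable case seen again, with small true shortfalls at pairs such as 5% v 10%.

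It is also fair that Fisher's test is itself conservative (actual size 0.9% at 10% v 10%). The gap between p = 0.038 and p = 0.110 therefore does not by itself show the t test to be in error. Finally, the protocol says that the study is inadequately powered, and these endpoints are secondary.

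**Conclusion.** The concern holds in a limited form. The Student t test is the only test named, and no method is specified for the between-arm incidence of rejection, graft loss and death. If the t test is used for them, it returns nothing when there are no events (13% to 61% of trials at equal assumed risks of 4% down to 1%). With one event in total its interval is 16 points wide, against 29 for Newcombe.

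The probabilities rest on assumed risks. At 10% per arm the 0 v 0 problem almost disappears and the t interval behaves well. Neither a general undercoverage claim nor a claim of inflated type I error is supported. The consequence is for secondary reporting in a pilot, not for a confirmatory conclusion. The mismatch between H0 and the continuous primary endpoint is real but separate, and adds nothing to the argument about sparse events.

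**What to change.** In the Statistical Analysis section:

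- For rejection by day 90 and by day 365, graft loss, and death, report counts and risks per arm and the risk difference with a 95% Newcombe or Miettinen-Nurminen interval, labelled descriptive. Name one of the two in advance, because they can fall on opposite sides of zero in a case such as 4 v 0.
- Limit the t test, or a mixed model over the planned time points, to the continuous C/D ratio and eGFR. Say which groups are being compared.
- Separately, restate H0 in terms of the continuous primary endpoint, for example equal mean C/D or eGFR between arms at a named time point.

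This needs no new patients, visits or data. The cost is a small wording change and wider intervals for the rare endpoints.

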Version Date: 11Jun2019 8 of 16 populations (race, sex, age, and diabetes) should provide evidence for possible greater efficiency and lesser toxicity of extended release drug, Envarsus, as compared to SOC treatment with immediate release tacrolimus given twice per day. Envarsus is an oral, extended-release formulation of tacrolimus developed to enable a once daily dosing regimen. It decreases intra-patient variability and offers flatter kinetics which should ensure a more consistent immunosuppression exposure over the long-term without unpredictable high peaks which may be related to higher toxicity rate, including nephrotoxicity. There is little doubt that the once daily dosing has been described as improving medication adherence [Sabbatini et al, 2014; Doesch et al, 2013; Eberlin et al, 2013; Kuypers et al, 2013].

Since Tacrolimus, the mainstay of immunosuppression in renal transplant patients is known for drug induced nephrotoxicity, which may limit graft survival we propose a prospective randomized study to analyze the relationship of tacrolimus doses to achieve target trough levels (C/D) and renal function at different time-points after transplantation. In this analysis, all 1:1 randomized renal allograft recipients maintained with mycophenolate sodium will be treated either with tacrolimus (Prograf) in the SOC treated controls or with Envarsus in the experimental group. Renal function will be estimated by MDRD equation (eGFR MDRD). Such a prospective, randomized, controlled pilot trial to compare the use of once a day Tacrolimus (Envarsus) vs. twice a day Tacrolimus (Prograf) to test the hypothesis that the consistency of immunosuppression with Envarsus increases the C/D ratio, i.e. get effective stable trough levels with lower total Tacrolimus dose given as Envarsus, and lead to better eGFR, and reduce the likelihood of nephrotoxicity (lower total Tacrolimus exposure). In the course of this study, patients in the control arm will receive immediate-release formulations of tacrolimus in accordance with local SOC dispensing practices, thus preserving the real-world conditions in which the patient could receive any manufacturer's approved product. In this manner, it is hoped that this research will improve the understanding of chronic calcineurin inhibitor injury and provide greater insight into how tacrolimus exposure impacts long term, and even short term, renal function (eGFR).

Pharmacokinetics

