This is an exploratory, pilot one year, prospective, randomized, open-label trial examining long-term kidney transplant outcomes. Specifically, it is designed to compare the effects of twice daily, immediate-release tacrolimus and once daily Envarsus on trough Tacrolimus concentrations (C) relative to the total daily dose (D) given and to determine the effect of C/D ratio on renal function at day 7 and months 1, 3, 6, and 12 months after transplantation utilizing concentration to dose ratio (C/D ratio). Patients will be screened prior to surgery and randomized 1:1 to receive, within 48 hours of transplantation, immediate-release tacrolimus, administered twice daily, or Envarsus once daily, as a component of a standard immunosuppression maintenance regimen also consisting of peri-transplant only corticosteroids and mycophenolate sodium (MPA), or equivalent. Induction therapy will be given and administered per center protocol. Intravenous corticosteroids will be administered prior to revascularization as part of the initial induction regimen, with dose and duration of therapy also determined by the standard protocol which tapers steroids off within 5 days of transplantation with few exceptions (patients who have been maintained on steroids prior to transplant and patients with IGA nephropathy). Thereafter, patients will be followed for up to 1 year during the open-label study period. Immediaterelease tacrolimus will be obtained from pharmacies per the local standard of care. After discharge from the hospital, the patients randomized to immediate-release tacrolimus will be permitted to receive any immediate-release tacrolimus product available to them through normal dispensing mechanisms. Envarsus will be supplied by Veloxis and dispensed by the Research Pharmacy. Additionally, all local kidney biopsy results, local laboratory results, AEs, and concomitant medications pertaining to AEs will be recorded. At the terminal study visit at 12 months, the most recently obtained lab results as well as any episodes of rejection, graft loss, and deaths occurring beyond the first year will be detailed and reported to the IRB. Pathology results [hematoxylin and eosin (H&E), light microscopy, and immunofluorescence] will be recorded when local kidney biopsies are performed and interpreted during the course of clinical care. Substantiation by local biopsy will be required for cases of suspected rejection. A kidney biopsy will be graded by the most recent version of the 2007 Update to the Banff '97 Classification by our renal pathologist blinded to clinical results.

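### The only null hypothesis is for an event probability, but the primary endpoint is continuous; no suitable method is specified for the C/D–eGFR relation, and none of its five time points is primary

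*Combined protocol and SAP*

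**What the plan says.** The combined protocol and SAP addresses the primary question in several places.

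- **Endpoints for Evaluation, Primary** (same wording in the Primary Objective). Two parts: the trough achieved relative to total daily dose, compared between Envarsus and immediate-release tacrolimus, "and the effect of C/D ratio on renal function at day 7 and months 1, 3, 6, and 12 months after transplantation". Study Design repeats the second aim: "to determine the effect of C/D ratio on renal function at day 7 and months 1, 3, 6, and 12 months after transplantation".
- **Endpoints for Evaluation, Secondary.** Incidence wording appears here: "Comparison between treatment cohorts regarding incidence will rely upon assessments". The list that follows covers rejection, graft loss, death and serious adverse events.
- **Background.** The trial is to "test the hypothesis that the consistency of immunosuppression with Envarsus increases the C/D ratio", and the same sentence expects better eGFR to follow.
- **Statistical Analysis, hypothesis.** "H0: The probability of incidence for the primary endpoint is the same between patients receiving Envarsus and patients receiving immediate-release tacrolimus".
- **Statistical Analysis, named test.** The efficacy analysis regarding "C/D effectiveness in relation to number of rejection episodes and outcomes at various stated time points will be conducted using Student T test".
- **Statistical Analysis, association.** "The association between whole blood concentrations and the following endpoints will be assessed: rejection episode and eGFR". The sentence goes on to histopathology and transplant outcomes and names no method.
- **Statistical Analysis, Sample Size.** The pilot is "not sufficiently powered to document that the C/D ratio in each patient group will correlate directly with eGFR".
- **Efficacy Assessment.** eGFR is calculated by four-variable MDRD at day 7 and months 1, 3, 6 and 12. C/D is calculated monthly.

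Study Design calls the trial an exploratory pilot. It is open-label, with 25 patients per arm. Formal Stopping Rules provides for an interim data analysis once all patients have completed 6 months. No significance level is stated.

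**The concern.** A hypothesis about the probability of an event needs an event. The primary endpoint has none: there is no responder rule, no C/D threshold and no eGFR cut-off. The stated hypothesis also differs from the one in Background, which concerns a higher C/D and a better eGFR.

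The second part of the primary endpoint asks how eGFR changes with C/D. The plan expects a correlation within each group but does not say how it will be estimated, and the association analysis it does promise uses blood concentration rather than C/D.

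The five time points have equal standing. The pilot's stated purpose is to find trends that guide a larger study. With the tested variable, the visit and the model all open, in an open-label trial with a 6-month look, each could be settled after results are seen. The reported trend would then depend partly on that choice.

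**Working it through.** There is no figure in the plan to reproduce: the sample size of 50 comes without alpha, power, effect size or SD. The check is a comparison of the texts and then two illustrations.

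**1. Hypothesis against endpoint.**
- The hypothesis compares a probability, which requires a yes/no outcome for each patient.
- Primary endpoint, part one: C/D, a concentration divided by a dose. Continuous.
- Primary endpoint, part two: the relation of C/D to MDRD eGFR. Both variables are continuous.
- An event definition for either part: none found.

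The hypothesis therefore has no quantity to act on.

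**2. Method against endpoint.** A two-sample t test can compare mean C/D, or mean eGFR, between two groups at one visit, so it can serve part one. It returns a difference in group means, not a slope, so it cannot serve part two.

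A simulation illustrates this (4,000 trials, 25 per arm, assumed C/D–eGFR correlation 0.5, equal mean C/D in both arms, assumed two-sided 0.05). A t test of eGFR by arm rejected in about 5% of trials, its null rate. A test of the slope of eGFR on C/D rejected in about 97%. In that setting the arm comparison carries no information about the relation.

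**3. Five unranked time points.** Assume each is tested between arms at two-sided 0.05, with no true difference. If visits are independent:

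1 − (1 − 0.05)^5 = 1 − 0.774 = 0.226.

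Repeated measures on the same patients are correlated, and the documents give no correlation, so a range is shown. It comes from 200,000 simulated null trials per setting, 25 per arm, equally correlated normal visits and two-sample t tests (simulation standard error below 0.001):

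| Assumed between-visit correlation | Chance of at least one false positive |
|---|---|
| 0 | 22.6% |
| 0.5 | 18.4% |
| 0.7 | 14.9% |
| 0.8 | 12.9% |

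One pre-named visit keeps the figure at 5%. In the endpoint text the five times attach to the effect of C/D on renal function; reading them as five arm comparisons is part of the assumption.

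**4. Day 7.** The endpoint needs C/D and eGFR at day 7. Efficacy Assessment provides eGFR then, but C/D only monthly, and post-transplant visits in the Schedule of Events begin at month 1. Troughs are among the routine laboratory values listed, so a day-7 C/D is probably recoverable, but the text does not provide for it.

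**The case against.** The strongest reply is that this is a declared pilot. The Sample Size text disclaims power and says significance is unlikely, so no confirmatory decision rests on the hypothesis, and a familywise error rate matters little where only trends are sought. That stands as far as error control goes. It does not make an undefined hypothesis testable or supply a missing method.

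Three stronger readings are tempting, and the documents do not support them.

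- *The plan assigns the wrong test to C/D versus eGFR.* It never expressly does so. The t test is attached to C/D in relation to rejection episodes and unspecified outcomes. The fault is an omission.
- *The plan does not contemplate a C/D–eGFR association at all.* The Sample Size text refers to exactly that correlation, by group. It names no method.
- *The trial carries a type I error of up to 23%.* The plan states no alpha and makes no claim conditional on a test.

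One might also take the hypothesis as meant for rejection, where incidence wording belongs. But it names the primary endpoint, and rejection is secondary.

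Finally, making C/D the single formal test may seem to sideline eGFR, which is in the trial's title and in the expected trend. That is a fair point of preference. Between-arm eGFR remains reported, as an estimate with its interval.

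**Conclusion.** The hypothesis is wrong as written: it cannot be tested on the primary endpoint and does not match the hypothesis in Background. This follows from the text alone. The second part of the primary endpoint has no suitable analysis specified, and no time point is primary.

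The 13% to 23% range rests on an assumed two-sided 0.05, arm comparisons at all five times and assumed between-visit correlations of 0.8 down to 0. It measures the scope for selective emphasis. This should be fixed, since the trends are meant to shape a larger trial, but it does not invalidate the pilot.

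**What to change.** Amend before the 6-month interim analysis.

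1. **Hypothesis.** Replace it with: no difference between arms in mean C/D (log scale suggested) at one pre-named visit, with the choice of visit justified. Report the other visits, and eGFR between arms, as estimates with 95% confidence intervals.
2. **C/D–eGFR relation.** Keep it in the primary objective as estimation. Fit a mixed model of eGFR on C/D, visit, arm, donor type (living or deceased) and C/D-by-arm, with a random patient effect. Enter C/D as the patient's mean and the deviation from that mean, so that between-patient and within-patient effects are separated. Report a slope and 95% confidence interval per arm, which matches the by-group relation in the Sample Size text. Label it a non-randomised association, because the Treatments section has dose titrated to blood levels and tolerability.
3. **Day 7.** Reconcile the monthly C/D calculation with the day-7 time point: either take day-7 C/D from routine trough and dose records, or limit the model to months 1, 3, 6 and 12.

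Cost: one written amendment, with sponsor and investigator approval and IRB approval or notification, under Protocol Amendment and/or Revision. No added patients or visits. The other visits lose formal tests, and the per-arm slopes will be imprecise with 25 patients in each arm.
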